- 7.4 Study treatment with pembrolizumab may be administered up to 3 days before or after the scheduled Day 1 of each cycle due to administrative reasons.
- 7.5 For this protocol, the patient must return to the consenting ACCRU institution for evaluation day 1 of cycles 2, 3, 5, 7, 9, 11, 13, 15, 17 and 19 (see Section 4.0 Test

Schedule, Active Monitoring Phase).

- 7.6 Treatment with study-specific drugs by a local medical doctor (LMD) is not allowed.
- 7.7 Patients who develop PD in the CNS only may receive radiotherapy and continue treatment on study after completion of radiotherapy. Patient must be clinically stable and have been off systemic corticosteroids for at least 14 days at the time of recommencement of treatment. **NOTE: Both lenvatinib and pembrolizumab should be withheld for a minimum of 3 days prior to radiation and for 3 weeks after radiation.**
- 7.8 Accumulating evidence indicates a minority of patients treated with immunotherapy may derive clinical benefit despite initial evidence of PD. Patients receiving treatment in this study will be permitted to continue treatment beyond initial PD, if the initial PD happens in the first 12 weeks post-registration (by RECIST 1.1), as long as they meet the following criteria:
- Investigator-assessed clinical benefit (e.g. absence of rapid disease progression and absence of progressive tumor at a critical anatomic site that requires urgent alternative intervention), and
 - The patient is tolerating study drug.
 - Patient does not continue to progress at 4 week follow-up imaging after PD first noted.

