- 9.6 Apart from the assigned study drugs, subjects are **prohibited from receiving the following therapies** during the Screening and Treatment Phase (including retreatment for post-complete response relapse) of this trial:
- 9.61 Antineoplastic systemic chemotherapy or biological therapy
 - 9.62 Immunotherapy not specified in this protocol
 - 9.63 Chemotherapy not specified in this protocol
 - 9.64 Investigational agents other than pembrolizumab and lenvatinib
 - 9.65 Radiation therapy. NOTE: Radiation therapy to a symptomatic solitary lesion or to the brain may be allowed at the investigator's discretion.
 - 9.66 Live vaccines within 30 days prior to the first dose of trial treatment and while participating in the trial. Examples of live vaccines include, but are not limited to, the following: measles, mumps, rubella, varicella/zoster, yellow fever, rabies, BCG, and typhoid vaccine.

- 9.67 Systemic glucocorticoids for any purpose other than to modulate symptoms from an event of clinical interest of suspected immunologic etiology. The use of physiologic doses of corticosteroids may be approved after consultation with the ACCRU Quality Assurance Specialist (see protocol resource page).
- 9.68 Subjects who, in the assessment by the investigator, require the use of any of the aforementioned treatments for clinical management should be removed from the trial. Subjects may receive other medications that the investigator deems to be medically necessary.

The Exclusion Criteria describes other medications which are prohibited in this trial.

There are no prohibited therapies during the Post-Treatment Follow-up Phase.

9.7 Pneumonitis:

For **Grade 2 events**, treat with systemic corticosteroids. When symptoms improve to Grade 1 or less, steroid taper should be started and continued over no less than 4 weeks.

For **Grade 3-4 events**, immediately treat with intravenous steroids. Administer additional antiinflammatory measures, as needed. Add prophylactic antibiotics for opportunistic infections in the case of prolonged steroid administration.

9.8 Type 1 Diabetes Mellitus (if new onset, including diabetic ketoacidosis [DKA]) or Grade 3 Hyperglycemia, if associated with ketosis (ketonuria) or metabolic acidosis (DKA)

For **T1DM** or **Grade 3-4 Hyperglycemia**

- Insulin replacement therapy is recommended for Type I diabetes mellitus and for Grade 3-4 hyperglycemia associated with metabolic acidosis or ketonuria.

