13.0 Treatment/Follow-up Decision at Evaluation of Patient

- 13.1 Patients who are CR, PR, or SD will continue treatment per protocol.
- 13.2 Patients who develop PD while receiving therapy or refuse treatment or choose alternative therapy will go to the event-monitoring phase per Section 18.0 and be followed every 180 days for a maximum of 3 years from study registration. (See exceptions in 13.5 and 13.6.)
- 13.3 Patients who go off protocol treatment for reasons other than those listed in Section 13.2 above (e.g., adverse events, other complicating disease) will go to Observation and will follow the test schedule (Section 4.0) every 84 days for a maximum of 3 years from study registration. If they progress or choose alternative therapy while in Observation, they will go to the event-monitoring phase.
- 13.4 OBSERVATION: The study treatment period is 54 weeks (19 cycles). Patients who are receiving clinical benefit (i.e., in CR or PR or SD) and who are tolerating treatment at the end of the study treatment period may continue on therapy for an additional 12 months. After study treatment has been discontinued, they should be observed every 12 weeks until PD or a maximum follow-up of 3 years from study registration. Once the patient has PD during observation, they will be followed in the event-monitoring phase for a maximum follow-up of 3 years from study registration (see Section 18.0). Subsequent treatment is at the discretion of their attending physician. NOTE: If the patient continues for an additional 12 months of treatment beyond the initial 54 weeks, the patient should follow the same test schedule, per protocol, as is done during the initial 54-week period.
- 13.5 Patients who develop PD in the CNS may receive radiotherapy and continue treatment on study after completion of radiotherapy. **NOTE: Both lenvatinib and pembrolizumab should be withheld for a minimum of 3 days prior to radiation and for 3 weeks after radiation.**

13.6 Accumulating evidence indicates a minority of patients treated with immunotherapy may derive clinical benefit despite initial evidence of PD. Patients receiving treatment in this study will be permitted to continue treatment beyond initial PD, if the initial PD happens in the first 12 weeks post-registration (by RECIST 1.1), as long as they meet the following criteria:

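### Sections 7.7 and 13.5 set different conditions for continuing study treatment after CNS progression, and Section 13.2 points to the looser one

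*Combined protocol and SAP*

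**What the plan says.** Section 7.7, under Protocol Treatment, states: "Patients who develop PD in the CNS only may receive radiotherapy and continue treatment on study after completion of radiotherapy". It then sets two conditions for restarting: "Patient must be clinically stable and have been off systemic corticosteroids for at least 14 days at the time of recommencement of treatment". A note adds: "Both lenvatinib and pembrolizumab should be withheld for a minimum of 3 days prior to radiation and for 3 weeks after radiation".

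Section 13.5, under Treatment/Follow-up Decision at Evaluation of Patient, states: "Patients who develop PD in the CNS may receive radiotherapy and continue treatment on study after completion of radiotherapy". The same note on withholding both drugs follows. The word *only* is absent, there is no requirement on stability or corticosteroids, and there is no reference to 7.7.

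Section 13.2 sends patients who progress on therapy to event monitoring every 180 days, subject to this pointer: "See exceptions in 13.5 and 13.6". It does not mention 7.7.

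Section 13.6, repeated in 7.8, is a separate exception for early progression. It applies "if the initial PD happens in the first 12 weeks post-registration (by RECIST 1.1), as long as they meet the following criteria", and three criteria are then listed.

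**The concern.** Both sections answer one question: may a patient whose disease has progressed in the CNS go back on lenvatinib and pembrolizumab after radiotherapy? They answer it differently. A site deciding what to do at progression will naturally work from Section 13, and the pointer in 13.2 takes it to the version without the conditions.

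At stake is who is re-exposed to both drugs after progression. The choice also sets the follow-up track: a patient who continues stays on the treatment test schedule with its imaging and adverse event assessments, while one who stops for progression goes to event monitoring. If sites rely on different sections, similar patients will be handled differently, and a monitor could record a deviation from 7.7 at a site that did what 13.5 allows.

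**Working it through.** No arithmetic in the plan depends on this rule, so the check is a side-by-side reading of 7.7 and 13.5, followed by a search for other text that closes the gap.

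**Step 1: compare the two rules.**

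| Element | Section 7.7 | Section 13.5 |
|---|---|---|
| Site of progression | CNS only | CNS |
| Clinical stability at restart | Required | Not mentioned |
| Time off systemic corticosteroids at restart | At least 14 days | Not mentioned |
| Hold of both drugs around radiation | At least 3 days before, 3 weeks after | Same |
| Reference to the other section | None | None |

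The shared note on the radiation hold shows that these are two statements of one rule. They differ in three elements.

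**Step 2: look for text that supplies the missing conditions.**

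- Section 9.65 exempts some radiotherapy from the list of prohibited treatments: "Radiation therapy to a symptomatic solitary lesion or to the brain may be allowed at the investigator's discretion". It sets no CNS-only limit, stability requirement or steroid-free interval.
- Section 9.67 prohibits systemic glucocorticoids on treatment, except for events of suspected immunologic origin. Physiologic doses may be approved after consultation. Section 9.68 says that patients who need a prohibited treatment should be removed from the trial. Neither sets a steroid-free interval before restart.
- Section 13.6 covers initial progression in the first 12 weeks only, on its own criteria.

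**Step 3: run the possible cases through both rules.**

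| Case | 7.7 | 13.5 as worded | Other text |
|---|---|---|---|
| CNS-only progression; stable and at least 14 days off steroids at restart | May continue | May continue | Rules agree |
| CNS-only progression; not stable, or less than 14 days off steroids, at restart | Must wait until the conditions are met | No bar | 9.67 and 9.68 restrict steroid use but give no interval |
| CNS plus extracranial progression, first 12 weeks | Outside its scope | Within its wording | 7.8 and 13.6 give a separate route |
| CNS plus extracranial progression, after week 12 | Outside its scope | Within its wording | 13.6 does not apply |

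The rules diverge, with nothing else to settle the matter, in the second and fourth rows.

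**Step 4: see whether the radiation hold makes the steroid condition redundant.** Both sections allow restart no earlier than 3 weeks (21 days) after radiation. For a patient to be 14 days steroid-free on that day, steroids must have stopped by day 21 − 14 = 7 after radiation. If they stop later than day 7, 7.7 delays restart beyond day 21 and 13.5 does not. The hold therefore does not replace the condition.

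**Step 5: check the direction.** Every patient who meets 7.7 also meets 13.5. The reverse fails in the two divergent rows, so the conflict runs one way.

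**The case against.** The strongest reply is that 13.5 is a shortened restatement. Section 7 governs treatment and holds the full rule, both texts are permissive, and nothing in 13.5 waives 7.7. A careful site that reads both would apply the stricter one. This stands in part: the rules are not mutually exclusive, and obeying 7.7 never breaches 13.5. But 13.5 does not cite 7.7, and 13.2 cites only 13.5 and 13.6. The neighbouring rule on early progression is repeated in Section 13 with all its criteria, so abbreviation is not the pattern there.

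It can also be said that extracranial progression triggers 13.2 in its own right, and that 13.5 was never meant to excuse it. That is a reasonable reading of intent. It is also what the word *only* in 7.7 makes explicit and 13.5 leaves open.

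Several stronger readings are tempting, and the documents do not support them:

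- A reader might infer that 7.7 excludes unstable or steroid-treated patients. It does not. Its test applies at recommencement, so it defers them. Only progression outside the CNS takes a patient out of its scope.
- A reader might infer that 13.5 leaves a patient on steroids for CNS disease free to resume. Sections 9.67 and 9.68 already restrict that use. What 7.7 alone adds is the 14-day interval.
- A reader might infer that every patient with CNS progression and disease elsewhere is affected. Section 7.7 limits where *progression* occurs. CNS-only progression with stable disease at other sites falls within both rules.
- A reader might infer that PFS is compromised. Section 16.32 takes the first of progression or death and makes no CNS exception, so the PFS date is fixed whether or not treatment continues.

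**Conclusion.** The inconsistency is real and should be corrected. Section 13.5 lacks three limits found in 7.7, and 13.2 directs the reader to 13.5. A site following 13.5 can breach 7.7 in two cases: CNS plus extracranial progression after week 12, and restart in a patient who is not clinically stable or is less than 14 days off systemic corticosteroids.

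The effect is on which patients resume both drugs after progression and which follow-up track they enter. The sample sizes and decision rules in Section 16 are unchanged. Adverse event evaluability in 16.31 depends only on having started treatment, so those denominators do not move either.

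The number of patients cannot be estimated, because the documents give no rate of CNS progression. Maximum accrual is 60 (Section 16.21), and known active CNS metastases are excluded at entry (Section 3.29g), so the group is probably small.

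The conclusion assumes that sites apply each section as worded. It takes no position on which conditions are clinically right.

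**What to change.** Reconcile 7.7 and 13.5 to a single set of conditions covering the site of progression, clinical stability and corticosteroid use at restart. State the rule in full in one section and have the other refer to it. Align the pointer in 13.2 so that a reader starting from Section 13 reaches the full rule. The sponsor decides which conditions apply.

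No added statement on the PFS date is needed, since 16.32 already settles it. The cost is protocol wording only; no analysis, sample size or decision rule changes.

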- Investigator-assessed clinical benefit (e.g. absence of rapid disease progression and absence of progressive tumor at a critical anatomic site that requires urgent alternative intervention), and
- The patient is tolerating study drug.
- Patient does not continue to progress at 4 week follow-up imaging after PD first noted.

Patients with initial progression will be assessed with clinical judgment as to whether the patient is deriving clinical benefit from treatment and should continue study treatment or discontinue and enter the follow up/survival phase of the study. If progression is confirmed then the date of disease progression will be the first date the patient met the criteria for progression based on the standard RECIST 1.1 criteria.

13.7 A patient is deemed *ineligible* if after registration, it is determined that at the time of registration, the patient did not satisfy each and every eligibility criteria for study entry. The patient may continue treatment off-protocol at the discretion of the physician as long as there are no safety concerns, and the patient was properly registered. The patient will go directly to the event-monitoring phase of the study (or off study, if applicable).

- If the patient received treatment, all data up until the point of confirmation of ineligibility must be submitted. Event monitoring will be required per Section 18.0 of the protocol.
- If the patient never received treatment, on-study material must be submitted. Event monitoring will be required per Section 18.0 of the protocol.

13.8 A patient is deemed a *major violation*, if protocol requirements regarding treatment in cycle 1 of the initial therapy are severely violated that evaluability for primary end point is questionable. All data up until the point of confirmation of a major violation must be submitted. The patient will go directly to the event-monitoring phase of the study. The patient may continue treatment off-protocol at the discretion of the physician as long as there are no safety concerns, and the patient was properly registered. Event monitoring will be required per Section 18.0 of the protocol.

13.9 A patient is deemed a *cancel* if he/she is removed from the study for any reason before any study treatment is given. On-study material and Off-Treatment Form must be submitted. Event monitoring will be required per protocol (Section 18.0).

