16.2 Sample Size/Accrual Rate

16.21 Sample Size: A total of 25 evaluable Cohort 1 and 25 evaluable Cohort 2 patients will be accrued per study design (50 evaluable total), unless one or both cohorts of the study are permanently closed at the stage 1 analysis or undue

toxicity is observed. We anticipate accruing an additional 10 patients (5 Cohort 1, 5 Cohort 2) in order to account for ineligibility, cancellation, major treatment violation, or other reasons. Therefore, maximum accrual is 60 patients for this trial (30 for each Cohort).

16.22 Accrual Time and Study Duration: We expect to accrue about 3 patients per month to this trial. Therefore, the accrual period for this Phase II study is expected to be about 20 months. We anticipate that the study will take approximately 3 years to complete. This allows a 6 month follow-up for the final patient enrolled, along with data entry, data clean-up, and analysis.

16.3 Analysis of Secondary Endpoints for both Cohorts.

This study will assess multiple secondary endpoints, including adverse events, progression-free survival (PFS) and overall survival (OS). All these analyses will be done for each cohort separately. In addition, all primary/secondary data will be summarized by descriptive factors as well (i.e. prior treatment, etc.).

16.31 Adverse Events: All patients that have initiated treatment will be considered evaluable for assessing adverse events. The maximum grade for each type of adverse event will be recorded for each patient, and frequency tables will be reviewed to determine adverse event patterns. Only the grade 2+ adverse events will be assessed, regardless of relationship to the study treatment.

16.32 Progression-Free Survival (PFS): Defined as the time from registration to the first of either death due to any cause or progression. The distribution of PFS will be estimated using the method of Kaplan-Meier.

16.33 Overall Survival: Defined as the time from registration to death due to any cause. The distribution of survival time will be estimated using the method of Kaplan-Meier. Special attention will be paid to any registered patient who dies early (i.e., within 60 days) of initiating their treatment. Circumstances surrounding such early deaths will be classified as being either due to malignant disease, toxicity, other causes, or of unknown reasons.

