2. Submit only if applicable.
3. Complete at each evaluation during Observation (see Section 4.0).
4. Upload a copy of documentation of progression in RAVE on the Supporting Documentation Form.

Follow-up Material(s)

CRF	Event Monitoring Phase ¹			
	At PD	After PD q. 6 mos.	Death	New Primary
Patient Status: Survival and Disease Status Follow-up/Event Monitoring	X	X	X	At each occurrence
Adverse Events: Late	X	X		
Notice of New Primary				X
Consent Withdrawal 
 • Consent Withdrawal: Specimens Only • Consent Withdrawal: Clinical Follow-Up Only • Consent Withdrawal: All Follow-Up 	X ²	X ²	X ²	X ³
Lost to Follow-up	X ²	X ²	X ²	
ACCRU Deviation Form ²	X ²	X ²	X ²	

1. If a patient is still alive 3 years after registration, no further follow-up is required.
2. Submit only if applicable.

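### Routine adverse-event collection ends when a treated patient is found ineligible or in major violation, although off-protocol dosing may continue and the patient stays in the adverse-event denominator

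*Combined protocol and SAP*

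**What the plan says.** Sections 13.7 (ineligibility discovered after registration) and 13.8 (severe violation of the Cycle 1 treatment requirements) carry the same permission: "The patient may continue treatment off-protocol at the discretion of the physician as long as there are no safety concerns". Each then limits the data owed. For treated patients found ineligible, 13.7 says that "all data up until the point of confirmation of ineligibility must be submitted", and it sends them to event monitoring or, if applicable, off study. For major violations, 13.8 says: "All data up until the point of confirmation of a major violation must be submitted. The patient will go directly to the event-monitoring phase".

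Section 18.1 sets out the forms. In active monitoring, *Adverse Events: Solicited* and *Adverse Events: Other* are due at each evaluation during treatment, at end of treatment and in Observation. The event-monitoring table contains neither. Its only adverse-event form is "Adverse Events: Late", marked at PD and every 6 months after PD.

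Section 16.31 defines the analysis. On the denominator: "All patients that have initiated treatment will be considered evaluable for assessing adverse events". On the summary: "The maximum grade for each type of adverse event will be recorded for each patient, and frequency tables will be reviewed". On scope: "Only the grade 2+ adverse events will be assessed, regardless of relationship to the study treatment". It states no adverse-event window and no exposure adjustment.

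Section 10.32 exempts a list of common toxicities from expedited reporting up to grade 3 (hypertension only below grade 3) when they do not lead to hospitalization, but keeps them under routine reporting. Section 10.54 asks for case report forms for related grade 1-2 events and for all grade 3-4 events. Neither section excepts patients covered by 13.7 or 13.8.

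**The concern.** Safety of the combination is a secondary objective in both cohorts (2.21), and 16.31 meets it with crude proportions of patients by maximum grade. A crude proportion is interpretable only if every patient in the denominator is watched for as long as exposure lasts, or for a common stated window. Here a patient can remain exposed and remain counted after scheduled collection has ended. An event that occurs later and is never recorded makes that patient look event-free, so any error in the rate is downward.

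The arrangement is also the reverse of what one would expect. A patient who stops the drugs because of an adverse event goes to Observation (13.3), where the solicited and other forms are still due. A patient under 13.7 or 13.8 who keeps taking the drugs loses those forms.

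**Working it through.** **Which events are exposed.** Setting the sections side by side:

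- Serious events stay reportable under 10.4 up to 30 days after the last dose whatever the attribution, and later if at least possibly related. Deaths (10.321) and events of clinical interest (10.56) have their own rules. None of these excepts the 13.7 and 13.8 patients.
- Section 16.51 says that the study team learns of every grade 4 and 5 event in real time, and the waiver list in 10.32 never reaches grade 4.
- What remains is non-serious events, chiefly grade 2-3. For the toxicities on the 10.32 list, the routine forms are the only channel, and that is the channel that 13.7 and 13.8 cut off. These events fall within the grade 2+ scope of 16.31.

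**How many patients.** Section 16.21 adds 5 patients per cohort to the 25 evaluable. The plan's total reproduces: 2 × (25 + 5) = 60, or 30 per cohort. The plan does not say how many of the 5 would be treated and then continue off-protocol. The allowance also covers cancellations, and by 13.9 those patients receive no study treatment, so they are outside the 16.31 denominator. I therefore take k = 0 to 5 affected patients, with 5 of 30 (16.7%) as an assumed upper bound.

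**Effect on a crude rate.** Let p be the true proportion with an event, n the treated patients, k the affected patients, and f the share of affected patients with an event whose event is recorded. If affected patients have the same underlying risk as the others:

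recorded rate = p × [1 − (k/n)(1 − f)]

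The documents do not give f, so I show f = 0 (nothing captured) and f = 0.5. With n = 30:

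| k | Multiplier, f = 0 | Multiplier, f = 0.5 | A true 30% is recorded as |
|---|---|---|---|
| 0 | 1.000 | 1.000 | 30.0% |
| 1 | 0.967 | 0.983 | 29.0% to 29.5% |
| 2 | 0.933 | 0.967 | 28.0% to 29.0% |
| 3 | 0.900 | 0.950 | 27.0% to 28.5% |
| 5 | 0.833 | 0.917 | 25.0% to 27.5% |

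The 30% is illustrative; the plan gives no expected grade 2-3 rate for the combination. In patients, 30% of 30 is 9.0, recorded as 9.0 × 0.833 = 7.5 at the extreme. If 2 of the 5 extra patients were cancels, then n = 28 and k = 3, and the f = 0 multiplier is 1 − 3/28 = 0.893.

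If collection ran to the end of exposure, f would be 1 and the multiplier 1.000 for every k.

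**The case against.** The strongest reply has four parts.

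1. **Adverse-event reporting does not stop.** A reader might infer from 13.7 and 13.8 that it does. The documents do not support that: serious events, deaths, events of clinical interest and the late adverse-event form all continue, and 10.55 refers late events to a Forms Packet that is not part of these documents. This stands, and it confines the point to routine, non-serious collection.

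2. **Grade 4 events are protected.** A reader might infer that the suspension rule in 16.52 is weakened. If grade 4 events were lost, it would be: at a true 30% grade 4 rate, the chance of 3 or more among the first 10 is 0.617, and 0.537 with one patient wholly unobserved. But 10.4 and 16.51 keep most such events in view, so this stronger reading fails. The documents do not say whether off-protocol doses count for those reporting windows, which is why I say largely protected and not fully.

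3. **The event-monitoring columns may not be meant strictly.** Sections 13.2, 13.7 and 13.9 send patients without PD into event monitoring, and 13.2 follows patients there every 180 days. Read literally, the 18.1 table would give patients without PD no scheduled status form either. That is fair. Even so, on the generous reading, collection at each evaluation is replaced by a form about every six months, and nothing says that these reports enter the 16.31 tables.

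4. **An on-protocol window is a legitimate choice.** Events under off-protocol dosing can reasonably be kept out of the main table. This also stands, but 16.31 states no such window, and 10.54 points the other way.

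A reader might also infer that major-violation patients are those at highest risk of toxicity. Section 13.8 defines the category by doubtful evaluability for the primary endpoint and does not say what kind of treatment departure it is, so the documents give no basis for that.

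**Conclusion.** The point holds in a limited form. Sections 13.7 and 13.8 state a data cut-off that does not fit 10.32, 10.54 and 16.31, and the passages need reconciling. The result is possible understatement of non-serious event rates, mainly grade 2-3, in the crude maximum-grade tables. The size is modest: no effect if no such patient continues dosing, and a multiplier of 0.833 (nothing captured) or 0.917 (half captured) if the whole allowance of 5 per cohort is affected. Those bounds rest on assumed values of k and f, on equal underlying risk, and on 30 treated patients. They show what the text permits, not a bias that has been demonstrated. No sample size, significance level, power or primary-endpoint rule changes. This is a minor improvement worth making because each cohort is small enough for a few truncated records to show in the tables.

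**What to change.** Reconcile 13.7, 13.8 and 18.1 with 10.54 and 16.31:

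- In 13.7 and 13.8, state that the cut-off does not apply to adverse events: the existing *Adverse Events: Solicited* and *Adverse Events: Other* forms continue while the patient receives either study drug and through 30 days after the last dose.
- In the event-monitoring table in 18.1, add an entry for these forms for such patients.
- In 16.31, where the forms cannot be obtained (for example because the patient has gone off study), flag the patient as having truncated adverse-event follow-up and show the adverse-event table with and without such patients.

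The cost is a sentence in each of the two sections, one forms-table entry and one line in 16.31, plus some extra form submission for at most a few patients during off-protocol care. The change concerns data collection and tabulation only and alters no dose or clinical rule.
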